## **7.3 TREATMENT COMPLIANCE**

Compliance will be evaluated by whether or not the medication was always administered according to protocol for BI 836826.

For patients where the infusion schedule was not followed a listing with comments will be presented.

Furthermore, a listing will show all administrations of BI 836826 including also the administration of premedication Analgesic/Antipyretic, Glucocorticoid and Antihistamine as well as the dose changes and interruptions of ibrutinib.

## **7.4 PRIMARY ENDPOINTS**

The primary endpoints are the RP2D and the number of patients with DLTs in the MTD evaluation period. The number of patients with DLTs at each dose level will be presented for the MTD evaluation period for the MTD evaluation set and for the whole on-treatment period for the treated set separately.

The RP2D will either be the MTD or any lower dose, examined based on safety and efficacy criteria. The analysis of the MTD is based on a BLRM guided by the EWOC principle. Estimation of the MTD during the dose escalation phase of the study will be based upon the estimation of the posterior probability of the incidence of DLT in toxicity categories during the MTD evaluation period for all evaluable patients. The model to be used is specified in CTP Section 7.

The posterior probabilities that the toxicity rates of each dose level fall into the categories specified in CTP Section 7 estimated from the BLRM will be displayed graphically as well as in a table. This will be done for the MTD evaluation period as well as for the complete on-treatment period.

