After all patients in a cohort have either experienced a DLT or have been observed for at least one cycle (28 days) without experiencing a DLT, the Bayesian model will be updated with the newly accumulated data. The overdose risk will then be calculated for each dose, and escalation will be permitted to all doses which fulfil the EWOC criterion and the additional 100% escalation rule

If DLTs are observed in the first two consecutive patients of a previously untested dose level, subsequent enrollment to that cohort will be stopped. The BLRM will be re-run to confirm that the dose-level still fulfils the EWOC criterion. Based on this information, the SRC will

evaluate whether the next patients will be enrolled on the same dose level, or if they will be enrolled to a lower dose level.

Based on the model and on additional information, if available (PK, PD, patient profiles), the members of the SRC will reach a joint decision on the next dose level to be investigated. The SRC may also provide a recommendation for the size for the next dose cohort. However, the final decision on the next cohort size will be agreed mutually between the Sponsor and the CI.

The SRC may recommend stopping the dose finding phase after the criterion for MTD (see [Section 7.1](#)) is fulfilled. Further patients may be included to confirm this MTD estimate.

If a MTD is determined during dose escalation, the RP2D may be either the MTD or a lower dose. If no MTD is observed after escalation to the highest possible dose of 1400 mg, 1400mg or a dose below 1400 mg may be selected as RP2D. The RP2D will be a safe dose at which the intended clinical efficacy (e.g. one or more of the following are observed: ALC lowering effect, clinical CR, MRD negativity, effect on biomarkers). A minimum of 6 patients need to be evaluated at the RP2D..

During dose escalation, enrollment into the first dose cohort will be allowed only after the first patient in the cohort is evaluable for safety for a minimum of 3 days from the first administration (10 mg pre-dose) of BI 836826. Subsequent patients within this cohort and subsequent cohorts may be enrolled at any time.

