Enrollment into the next higher dose cohort is allowed after the previous dose cohort is found to be safe for all patients in this cohort by the SRC. For the purposes of determining dose escalation, DLTs will be assessed based on safety data from cycle 1. However, AEs including those qualifying for DLT will be monitored beyond cycle 1 and throughout the trial.

Treatment:

Ibrutinib is going to be dosed at fixed, approved dose of 420mg daily in all patients. Stepwise dose escalation of BI 836826 will be performed. BI 836826 will be administered in Cycle 1 on the following days: D1 (10mg), D2 and D8 (50% of the assigned dose on each day), D15 (100% of the assigned dose). In Cycle 2-4 BI 836826 will be administered at the assigned dose on days 1 and 15 of each cycle. In Cycle 5-12 BI 836826 will be administered at the assigned dose on day 1 only. Patients will continue the study treatment till disease progression, unacceptable toxicity, or withdrawal of consent. Continued monthly treatments beyond cycle 12 are possible for patients with a CR, CRi, or MRD negative PR in the response assessment at the end of Cycle 12. In such cases, patients may continue treatment with 12 additional cycles of combination treatment up to a maximum and total of 24 treatment cycles.

Patients will take two weeks of ibrutinib during the run-in phase, prior to start of BI 836826 and will continue ibrutinib throughout the whole duration of the study. After completion of the study the continued treatment with ibrutinib is left to the decision of the investigator or patient's physician, depending on patients' disease status, and the need for further treatment.

For selection of doses please refer to [Section 4.1.3](#).

For dose adaptation in case of AEs please refer to [Section 4.1.4.5](#).

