5.1.1 Primary endpoint(s)

One primary endpoint is to determine the RP2D of BI 836826 in combination with ibrutinib. If a MTD can be determined based on the criteria as described in [Section 7](#), the RP2D will be either the MTD or a lower dose. The RP2D will be determined based on safety and efficacy criteria. Safety criteria include, but are not limited to the number of DLTs during the first treatment cycle, other AE and laboratory abnormalities may be considered in addition. Efficacy criteria include, but are not limited to the effect of BI 836826 on ALC, lymph node size as assessed by SPD, improvement of decreased blood cell counts related to CLL at baseline, overall response. Biomarkers may be considered in addition.

The second primary endpoint is the number of patients with DLT during the first treatment cycle. The number of evaluable patients per dose level with DLTs will be used to update the Bayesian model and to eventually determine the MTD.

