7. STATISTICAL METHODS AND DETERMINATION OF SAMPLE SIZE

7.1 STATISTICAL DESIGN – MODEL

This trial will be performed as an open-label single-arm study. The primary objective of the trial is to determine the RP2D of BI 836826 in combination with ibrutinib. The RP2D will be either the MTD or a lower dose. To determine the MTD, patients are entered sequentially into escalating dose cohorts. The dose-finding will be guided by a Bayesian 5-parameter logistic regression model with overdose control ([R13-4806](#)), ([R13-4803](#)). This design is based on practical experience and is a preferable algorithmic method due to its superior ability to identify the dose with a desired toxicity rate and its allocation of a greater proportion of patients to doses at, or close to, that dose ([R13-4802](#), [R13-4804](#), [R13-4805](#)).

In the following, DLT denotes a dose-limiting toxicity occurring during the first cycle. The 5-parameter logistic regression model is defined as follows. Let $\pi_{1,d1}$ be the probability of having a DLT when giving dose d_1 of BI 836826, and $\pi_{2,d2}$ the probability of having a DLT when giving dose d_2 of ibrutinib, respectively. A logistic regression is used to model the dose-toxicity relationship for each of these drugs individually:

$$\begin{array}{ll} \text{BI 836826:} & \text{logit}(\pi_{1,d1}) = \log(\alpha_1) + \beta_1 \log(d_1/d_1^*) \\ \text{Ibrutinib:} & \text{logit}(\pi_{2,d2}) = \log(\alpha_2) + \beta_2 \log(d_2/d_2^*) \end{array}$$

Here, the doses $d_1^* = 200\text{mg}$ and $d_2^* = 420\text{mg}$ BBB represent the reference doses for BI 836826 and ibrutinib, respectively.

Under independence, the probability of a DLT when giving the combination dose d_1, d_2 is obtained as

$$\pi_{12,d1,d2}^0 = \pi_{1,d1} + \pi_{2,d2} - \pi_{1,d1}\pi_{2,d2}$$

with corresponding odds

$$\text{odds}(\pi_{12,d1,d2}^0) = \pi_{12,d1,d2}^0 / (1 - \pi_{12,d1,d2}^0)$$

In order to account for a potential positive (higher toxicity than expected under independence) or negative (lower toxicity than expected under independence) interaction between BI 836826 and ibrutinib, a dose-dependent interaction term $-\infty < \eta < \infty$ is introduced in the model:

$$\text{odds}(\pi_{12,d1,d2}) = \text{odds}(\pi_{12,d1,d2}^0) \exp(\eta \log(d_1/d_1^*) \log(d_2/d_2^*))$$

and $\pi_{12,d1,d2}$ is used in the likelihood

$$r_{d1,d2} \sim \text{Binomial}(n_{d1,d2}, \pi_{12,d1,d2})$$

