where $r_{d1,d2}$ denotes the number of DLTs observed in $n_{d1,d2}$ patients at dose combination d_1, d_2 . Since a Bayesian approach is applied, prior distributions f for each of the parameter vectors $\theta_1 = (\log(\alpha_1), \log(\beta_1))$, $\theta_2 = (\log(\alpha_2), \log(\beta_2))$ and for the interaction term η need to be specified.

The prior distributions for θ_k will be specified as a mixture of two bivariate normal distributions,

$$f(\theta_k) = a_{1,k} f_1(\theta_k) + a_{2,k} f_2(\theta_k)$$

with

$a_{1,k}, a_{2,k}$ the prior mixture weights ($a_{1,k} + a_{2,k} = 1$), $k=1,2$ and

$f_i(\theta_k) = \text{MVN}(\mu_{ik}, \Sigma_{ik})$ a bivariate normal distribution with mean vector μ_{ik} and covariance matrix Σ_{ik} where

$$\Sigma_{ik} = \begin{pmatrix} \sigma_{ik,11}^2 & \sigma_{ik,11}\sigma_{ik,22}\rho_{ik} \\ \sigma_{ik,11}\sigma_{ik,22}\rho_{ik} & \sigma_{ik,22}^2 \end{pmatrix}$$

Mixture prior distributions have the advantage that they allow for specification of different logistic dose-toxicity curves, therefore making the prior more robust. A weakly-informative normal prior distribution will be used for η .

The estimated probability of DLT at each dose level from the model will be summarized using the following intervals:

Under dosing: [0.00, 0.16)

Targeted toxicity: [0.16, 0.33)

Over dosing: [0.33, 1.00]

The BLRM-recommended dose for the next cohort is the level at which the probability for the target toxicity interval is maximal out of the dose candidates satisfying the escalation overdose control criterion EWOC. Per EWOC it should be unlikely (<25% posterior probability) that the DLT rate at the dose combination will exceed 0.33. The overdose control criterion requires the probability of overdosing to be below 0.25. However, the maximum allowable dose increment for the subsequent cohort will be no more than 100% for each drug

The MTD may be considered reached if the following criteria are fulfilled:

1. The posterior probability of the true DLT rate in the target interval [0.16 – 0.33) of the MTD is above 0.50, OR
2. At least 15 patients have been treated in the study, of which at least 6 at the MTD.

Prior derivation:

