To determine the prior distributions for $(\log(\alpha_1), \log(\beta_1))$ and $(\log(\alpha_2), \log(\beta_2))$, a meta-analytic predictive (MAP) approach will be used. Toxicity information on BI 836826 from the 1270.1 Phase I study and from two published studies of ibrutinib will be incorporated. Exact details on the derivation of the prior distributions and on the evaluation of the model using hypothetical data scenarios and operating characteristics are provided in the statistical appendix; a brief description is given here.

The historical data for BI 836826 can be found in [Table 7.1:1](#). For ibrutinib, the historical data can be found in [Table 7.1:2](#).

Table 7.1:1 Historical data for BI 836826

Study	Dose(mg)	N of DLTs during first cycle / N of patients
1270.1		
	1	0/3
	3	0/3
	9	0/6
	25	0/6
	50	0/3
	100	0/3
	200	1/6
	400	0/3
	800	1/2

Table 7.1:2 Historical data for ibrutinib

Study	Dose(mg)	N of DLTs / N of patients
Byrd et al*		
	420	2 / 51
	840	4 / 34
Advani et al**		
	87.5	0 / 7
	175	1 / 9
	350	0 / 6
	560	0 / 9
	581	1 / 18
	875	0 / 7

* No DLTs were reported for this study. The number of DLTs was therefore approximated by the number of AEs leading to discontinuation.

** Dosing based on mg/kg was used. The corresponding fixed dose was calculated as the dose corresponding to a weight of 70kg.

The following steps were used to derive the prior distributions for all parameters:

1. $\log(\alpha_1)$, $\log(\beta_1)$:
 - a. The meta-analytic-predictive prior was derived using the information in [Table 7.1:1](#), allowing for moderate to substantial between-trial heterogeneity. This mixture component was assigned 90% mixture weight.
 - b. A second, weakly-informative component was added with 10% mixture weight.
2. $\log(\alpha_2)$, $\log(\beta_2)$:
 - a. The meta-analytic-predictive prior was derived using the information in [Table 7.1:2](#), allowing for large to very-large between-trial heterogeneity. This mixture component was assigned 90% mixture weight.
 - b. A second, weakly-informative component was added with 10% mixture weight.
3. η : based on the a priori assumption of no interaction between the two compounds, a normal distribution with mean 0 and standard deviation 0.56 was chosen. At the starting dose combination, the corresponding 95% prior interval covers an up to 1.4 fold increase (or decrease) in the odds of DLT over no interaction.

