7.3.1 Primary endpoint analyses

RP2D and number of patients with DLTs in first cycle, measured from first administration of BI 836826 until the end of the first cycle. The number of patients with DLTs at each dose level will be presented (all cycles and cycle 1 separately).

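### SAP 7.4 shows the BLRM under-, target- and over-dosing probabilities for the complete on-treatment period, although the model's DLT, its BI 836826 prior data and the 0.16/0.33 limits are set for Cycle 1

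*SAP*

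**What the plan says.** SAP 7.4 (Primary endpoints) takes its model from protocol Section 7. It plans a graph and a table of the posterior probability that each dose's toxicity rate falls in each protocol category, and then states: "This will be done for the MTD evaluation period as well as for the complete on-treatment period". SAP 6.1 runs the on-treatment period from the first BI 836826 dose to 30 days after the last. The SAP gives no separate prior, limits, exposure handling or caveat for this second fit.

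Protocol 7.1 opens the model with "DLT denotes a dose-limiting toxicity occurring during the first cycle". The BI 836826 prior data in Table 7.1:1 are headed "N of DLTs during first cycle / N of patients". The categories are introduced by "The estimated probability of DLT at each dose level from the model will be summarized using the following intervals": under-dosing below 0.16, target from 0.16 to below 0.33, over-dosing from 0.33. The likelihood is binomial in patients per dose.

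Treatment is planned for 12 cycles. After that, for CR, CRi or MRD-negative PR, "patients may continue treatment with 12 additional cycles of combination treatment up to a maximum and total of 24 treatment cycles" (protocol 3.1).

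For DLTs beyond Cycle 1, protocol 7.3.1 plans patient counts by dose level and no model fit. SAP 5.2.2 and 7.5.2 restrict MTD determination to the MTD evaluation period and to evaluable patients.

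**The concern.** A limit of 0.33 on the chance of a DLT in one 28-day cycle and a limit of 0.33 on the chance of any DLT in a year or more of treatment are different standards. The plan uses the same number and the same label for both. The binomial likelihood also counts a patient followed for one cycle and a patient followed for 24 cycles as one observation each, so the on-treatment quantity depends on how long each cohort was treated.

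What is at stake is interpretation. The display sits in the primary-endpoint section beside the RP2D, whose criteria go wider than Cycle 1: "Safety criteria include, but are not limited to the number of DLTs during the first treatment cycle". A reader of the report would see two sets of over-dosing probabilities for the same dose. Nothing would say that the second set applies Cycle 1 limits to a longer and uneven window.

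**Working it through.** **Inputs.** Priors from protocol Table 7.1:3; the model and the 0.16/0.33 limits from protocol 7.1; ibrutinib fixed at 420 mg. Doses of 100, 200 and 400 mg are the first three provisional levels in protocol 4.1.3. Six patients at 400 mg matches protocol 3.1: "A minimum of 6 patients need to be evaluated at the RP2D". The late DLTs are assumed.

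**Method.** Draw the parameters from the mixture priors and weight each draw by the product over doses of π^r (1−π)^(n−r), where r is the number of DLTs in n patients. The probability of a category is the weighted share of draws with π in it. The run used 6,000,000 draws, with an effective sample size of at least 1.98 million in every six-patient case.

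**Interaction term.** As printed, it contains log(d2/d2*) = log(420/420) = 0, so η drops out. That form gives prior under/target/over at 400 mg of 0.227/0.340/0.433, against 0.305/0.232/0.463 in Table 7.1:4. Replacing the two logs by the dose ratios, η·(d1/200)·(d2/420), reproduces the table. This second form is inferred from that match. Results are given for both forms.

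**Reproducing the protocol's figures (ratio form).**
- Table 7.1:4, 200 mg: 0.445/0.313/0.242 (printed 0.448/0.312/0.241).
- Table 7.1:4, 400 mg: 0.302/0.234/0.464 (printed 0.305/0.232/0.463).
- Table 10.7:1, over-dosing at the current dose of 400 mg: scenario 13 gives 0.058 (printed 0.056); scenario 14 gives 0.286 (printed 0.284).

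**Illustration.** Cycle 1 data are held at 0/3, 0/3 and 0/6 at 100, 200 and 400 mg. Entries are P(under)/P(target)/P(over) at 400 mg.

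| DLTs after Cycle 1 | Ratio form | As printed |
|---|---|---|
| None | 0.845/0.139/0.017 | 0.716/0.260/0.024 |
| One at 400 mg | 0.539/0.358/0.103 | 0.450/0.453/0.097 |
| Two at 400 mg | 0.229/0.450/0.321 | 0.211/0.522/0.267 |
| One at 200 mg, one at 400 mg | 0.352/0.447/0.200 | 0.259/0.547/0.194 |

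One late DLT leaves over-dosing near 0.10. Under-dosing stays the most probable category in the ratio form; in the printed form target is marginally ahead (0.453 against 0.450). With two late DLTs target is the most probable category in both forms, and with both at 400 mg over-dosing rises to 0.27-0.32.

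**Scale mismatch without the model.** With a constant DLT risk per cycle, the risk at which the cumulative probability reaches limit L in c cycles is 1−(1−L)^(1/c).
- L = 0.33: 1−0.67^(1/12) = 3.28% per cycle over 12 cycles; 1−0.67^(1/24) = 1.65% over 24.
- L = 0.16: 1−0.84^(1/12) = 1.44% over 12 cycles; 1−0.84^(1/24) = 0.72% over 24.

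As Cycle 1 rates, all four lie far inside the under-dosing range.

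Starting instead from a Cycle 1 rate of 0.20 (Table 10.7:2, scenario 3, 400 mg), the later per-cycle risk at which the cumulative rate reaches 0.33 is 1−(0.67/0.80)^(1/(c−1)). That is 3.48% for c = 6 and 1.60% for c = 12. These are break-even values, not estimates.

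**The case against.** The strongest reply is that no decision rests on this display. The MTD uses only DLTs in the MTD evaluation period. SAP 6.1 presents DLTs from the two periods separately, so the Cycle 1 result is always visible. Development has been discontinued (protocol 2.1) and an abbreviated report is planned (SAP 3), so a misread panel cannot steer further escalation or a Phase II part. All of this stands, and it keeps the severity low.

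A summary of later toxicity also fits the protocol: DLT-type events are monitored beyond Cycle 1 (3.1), and the RP2D draws on all the safety data (7.3). That stands too. The fault is the labels, not the interest in late events.

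Three stronger readings are tempting, and the documents do not support them.
- A reader might infer that a dose could fail overdose control on this display. For example, with 0/3 at 100 mg and 1/6 at 200 mg, one late DLT at 200 mg raises over-dosing at 300 mg from 0.222 to 0.443 (ratio form), past the 0.25 limit. SAP 7.4 attaches no such decision to the on-treatment fit.
- A reader might infer that longer treatment alone moves the probabilities. It does not. With no exposure term, only additional DLTs shift the posterior, and those are real drug-related toxicity.
- A reader might infer that the whole prior is first-cycle. Only the BI 836826 data are labelled so. The ibrutinib data in Table 7.1:2 are not, and one of those studies uses AEs leading to discontinuation as a proxy for DLTs.

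The constant-risk break-evens are also a simplification, since BI 836826 infusions become less frequent from Cycle 5.

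**Conclusion.** The point holds as one about interpretation and labelling. Followed as written, SAP 7.4 grades cumulative DLT risk over unequal follow-up with limits set for a Cycle 1 rate, and nothing in either document adapts or qualifies them. MTD determination and the planned DLT counts are unaffected.

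The size depends entirely on how many DLTs occur after Cycle 1, and the documents give no rate for that, so no frequency is claimed. In the six-patient illustration, over-dosing at 400 mg moves from about 0.02 to 0.10 with one late DLT and to 0.27-0.32 with two, with Cycle 1 toxicity unchanged. The direction and rough size are the same under both forms of the interaction; whether target becomes the most probable category after a single late DLT differs between them. Low severity, but worth correcting because the correction is so small.

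**What to change.** In SAP 7.4, limit the BLRM category table and figure to the MTD evaluation period and the MTD evaluation set. Report on-treatment DLTs as the counts by dose already planned for the treated set, with cycles received by dose beside them from the SAP 7.7 exposure summary.

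If the on-treatment fit is kept, either drop the under-, target- and over-dosing labels or mark it exploratory. The footnote should then say that the model's DLT definition, the BI 836826 prior data and the 0.16/0.33 categories refer to Cycle 1, and that length of follow-up is not accounted for. It should not say that the whole prior was set for Cycle 1.

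The cost is one SAP sentence or one footnote, and one supportive display lost or relabelled. No information on late toxicity is lost, because the counts and exposure are already planned.

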## **7.5 SECONDARY ENDPOINTS**

### **7.5.1 Key secondary endpoints**

Not applicable.

### **7.5.2 Other Secondary endpoints**

The secondary endpoint is the MTD. This will be analysed analogously to the primary endpoint RP2D. Only patients evaluable for MTD determination will be used for the analysis of the MTD, i.e. patients, if any, who were replaced during the MTD evaluation period will be excluded from the analysis of the MTD.

## **7.7 EXTENT OF EXPOSURE**

Standard descriptive analyses over all treatment courses will be performed. This will include a summary of the variables already described in [Section 5.4.2](#). This descriptive analysis will comprise a mixture of frequencies and percentages, as well as summary statistics.

## **7.8 SAFETY ANALYSIS**

If not specified otherwise, all safety analyses will be performed on the treated set.

